A newer design that attempts to address these issues is the medial pivot knee (MP). This design is characterized by an asymmetrical tibial insert in which the medial compartment is ultra-congruent, providing antero-posterior stability and the lateral compartment allows for rollback around a medial axis of rotation i.e uses a ball-and-socket mechanism. (20) This design more accurately recreates normal knee kinematics, reduces anteroposterior instability, and avoids condylar lift-off (21-24). Early studies indicate improved polyethylene wear characteristics (25). Midterm studies report excellent implant survivorship and clinical outcomes (26, 27).

Several randomized trials have compared the MP knee favorably with other designs. Patients with bilateral TKAs with a different prosthesis on each side preferred their medial pivot knee to a PS, CR, or mobile-bearing (MB) design (28). A trial comparing the MP and PS designs found greater range of motion (ROM) and better patient-reported outcomes in the MP group at 2 years (29). There also exists literature reporting poorer outcomes with the MP design. A trial involving 96 patients who had received both an MP knee and an MB knee on contralateral sides found lower ROM, higher complication rates, and worse patient reported outcomes in the MP knee (30).

Given the lack of consensus in the literature, further investigation is warranted to determine the impact of the MP design on outcomes following TKA.

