5.0 STUDY DESIGN & METHODS

50 patients will be recruited over 12-18 months. Half of the patients will receive the Medacta GMK Sphere prosthesis (Ball-and-socket), while the other half will receive the Medacta GMK posterior stabilized prosthesis (Cam-and-post). Patients will be randomized in the operating room through the opening of opaque, study-numbered envelopes prior to skin incision.

Patient-reported outcomes will be administered pre-operatively, immediately post-operatively, 6 weeks post-operatively, 3 months post-operatively, 6 months post-operatively, 12 months post-operatively, and 2 years post-operatively. Patient-reported outcomes will be measured using the Oxford knee score (see appendix 1), Knee Society Score, VR-12 (see appendix 2), the Forgotten Joint Score (FJS) for the knee (see appendix 3), and the Kujala Scoring Questionnaire (see appendix 4) as well as the physical function, pain interference, and pain behavior PROMIS CATs (see appendix 5). These questionnaires will be completed at the routine post-operative clinic visits or over the phone through PROMIS Assessment Center. The Forgotten Joint Score (FJS) will only be administered at the subject's 12 month post-operative time point and the Kujala Scoring Questionnaire will only be administered at the subject's 2 year post-operative time point.

At 3-6 months post-op, the operative knee will be examined by a single Sports Orthopaedics attending surgeon [name], who is an expert in assessing knee stability. The attending will grade the stability of the knee in various degrees of flexion according to section 4 of the International Knee Documentation Committee's Knee Ligament Standard Evaluation Form (see appendix 3). KT1000 arthrometer (MEDmetrics, San Diego, CA) measurements will also be taken by a single provider at the 3-month postoperative visit. The patient will also be graded on the get-up-and-go test at this time.

A prospective chart review will be performed starting at the time of enrollment and ending at the study completion date to obtain and verify the following data from NMH Medical records (PRIMES, Cerner PowerChart) and NMFF Medical Records (EpicCare, IDX/GE Centricity):

- EPIC Number
- MRN
- Medical History
- Medications
- Surgical History
- Date of Surgery
- Time taken to complete surgery
- Type of implant

- Post operative quality of prosthesis position/fixation
- Pre and post-operative lab values (Hg, plts, WBC, ESR, CRP, INR, etc)
- Complications/Reoperations

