6.0 STATISTICAL PLAN

This proposed sample size is small enough to feasibly recruit over the given time period, yet large enough to correlate differences between the two groups.

Data Cleaning and Crosschecking:

Data cleaning and crosschecking will be conducted prior to analyses. These procedures will include: 1) Comparing patient counts with accrual records; 2) Grouping data by assessment and ensuring a match with the designated number of assessments; 3) Cross-checking baseline and follow-up assessment dates; 4) Ensuring correct questionnaire count match to electronic data fields; 5) Summarizing missing data and checking for definable patterns.

Statistical Analysis:

This study has the primary objective of comparing outcome measures between the MP and PS knee prostheses. We will calculate descriptive statistics for the patient characteristics and measures obtained from each group (means, SD, range). We will use the Shapiro-Wilk test to identify whether each continuous variable fits a normal distribution. We will then use a two-tailed Student's t test for parametric data or the Mann-Whitney U test for nonparametric data to compare the two cohorts. The Pearson χ^2 or Fischer's exact test will be used for categorical variables where appropriate. The level of significance will be defined at $p < 0.05$.

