	ALL OF THE TIME	MOST OF THE TIME	A GOOD BIT OF THE TIME	SOME OF THE TIME	A LITTLE OF THE TIME	NONE OF THE TIME
a. Have you felt calm and peaceful ?	1	2	3	4	5	6
b. Did you have a lot of energy ?	1	2	3	4	5	6
c. Have you felt downhearted and blue ?	1	2	3	4	5	6

7. During the past 4 weeks, how much of the time has your physical health or emotional problems interfered with your social activities (like visiting with friends, relatives, etc.)?

ALL OF THE TIME	MOST OF THE TIME	SOME OF THE TIME	A LITTLE OF THE TIME	NONE OF THE TIME
1	2	3	4	5

Now, we'd like to ask you some questions about how your health may have changed.

8. Compared to one year ago, how would you rate your **physical health** in general now?

MUCH BETTER	SLIGHTLY BETTER	ABOUT THE SAME	SLIGHTLY WORSE	MUCH WORSE
1	2	3	4	5

9. Compared to one year ago, how would you rate your **emotional problems** (such as feeling anxious, depressed or irritable) **now**?

MUCH BETTER	SLIGHTLY BETTER	ABOUT THE SAME	SLIGHTLY WORSE	MUCH WORSE
1	2	3	4	5

3. IKDC Knee ligament standard evaluation form

THE IKDC KNEE LIGAMENT STANDARD EVALUATION FORM *[1]

Name: _____ first name: _____ DOB: ____/____/____ med. rec. #: _____
 Examiner: _____ date of examination: ____/____/____ date of injury/les: ____/____/____ date of surgeries: ____/____/____
 Cause of injury: ADL*[2] traff. non-pivoting non-contact sports pivoting non-contact sp. contact sp. work
 Time inj. to surg. : _____ (months) acute (0-2 weeks) subacute (2-8 weeks) chronic (>8 weeks)
 Knee involved: r. l. opposite knee: norm. injured exam. under anesth.: yes no
 Postop. diagnosis: _____
 Surgical proced.: _____
 Status menisci: norm med. lat. 1/3 removed: med. lat. 2/3 removed: med. lat. compl. rem. med. lat.
 Morphotype: lax normal tight varus valgus
 Activ.level*[3]: preinjury: I II III IV pretreatment: I II III IV
 present: I II III IV Eventual change knee-related: yes no

GROUPS (PROBLEM AREA)	QUALIFICATION WITHIN GROUPS *[4]				GROUP QUALIFC. A B C D*[4]
	A: normal	B: nearly norm.	C: abnormal	D:sev. abnorm.	

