4. LIGAMENT EXAMINATION *[8]					
Δ *[7] Lachman (in 25°. flex.)*[9]  -1 to 2mm  -1 to-3mm  or <-3mm  >10mm					
idem (alternative measurement, optional)  -1 to 2mm  3-5/-1 to-3mm  6-10/-<-3mm  >10mm					
Endpoint:  firm  soft					
Δ *[7] total a.p.transl. in 70° flex.*[9]  0 to 2mm  3 to 5mm  6 to 10mm  >10mm					
idem (alternative measurement, optional)  0 to 2mm  3 to 5mm  6 to 10mm  >10mm					
Δ *[7] post. sag in 70° flex.  0 to 2mm  3 to 5mm  6 to 10mm  >10mm					
Δ *[7] med. joint opening (valgus rotation)  0 to 2mm  3 to 5mm  6 to 10mm  >10mm					
Δ *[7] lat. joint opening (varus rotation)  0 to 2mm  3 to 5mm  6 to 10mm  >10mm					
Pivot shift *[11]  neg.  + (glide)  ++ (clunk)  +++ (gross)					
Δ *[7] reversed pivot shift  equal(neg.)  slight  marked  gross					   

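### The Lachman row of IKDC section 4 downgrades a knee for being tighter as well as looser, so as a stability measure it can hide or reverse a real difference between implants

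*Combined protocol and SAP*

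**What the plan says.** Section 5.0 plans one manual stability examination at 3 to 6 months: "the operative knee will be examined by a single Sports Orthopaedics attending surgeon", and "The attending will grade the stability of the knee in various degrees of flexion according to section 4" of the IKDC form in Appendix 3. KT1000 arthrometer readings by a single provider are planned at the 3-month visit.

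On the form, section 4 (Ligament Examination) prints these Lachman bands: A, -1 to 2 mm; B, 3 to 5 mm or -1 to -3 mm; C, 6 to 10 mm or below -3 mm; D, above 10 mm. The form labels A to D as normal, nearly normal, abnormal and severely abnormal. Total a.p. translation and posterior sag at 70 degrees, and medial and lateral joint opening, have bands that start at 0 mm. The form's header also records the state of the other knee: "opposite knee: norm. injured".

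Section 1.0 says of the MP design: "This design more accurately recreates normal knee kinematics, reduces anteroposterior instability, and avoids condylar lift-off". Section 6.0 says that a Pearson chi-square or Fisher's exact "test will be used for categorical variables where appropriate", with t or Mann-Whitney tests for continuous measures. It has no rule for the sign of the Lachman difference.

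**The concern.** The Lachman row measures departure from a reference knee in either direction. The trial asks a one-directional question: which implant leaves the knee more stable. One of the two implants is expected to reduce anteroposterior motion.

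If that implant takes some knees below the laxity of the opposite knee, the row marks them down for the effect under study. The grades could then look alike when laxity differs, or could favour the looser implant. If only the box is ticked, tight and loose downgrades cannot be separated later.

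**Working it through.** **Step 1: the bands in whole millimetres (Appendix 3, section 4).** -1 to +2 is A. -2 and -3 are B, as are +3 to +5. -4 or lower is C, as are +6 to +10. +11 or more is D, with no negative counterpart. So a knee 4 mm tighter is C, while one 2 mm looser is A. The row is not monotone in laxity. As printed, -1 mm falls in both A and B; here it is scored A.

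**Step 2: inputs for an illustration.** The documents give no mean, SD or effect size for laxity, so these are assumptions: a normal side-to-side difference with mean μ and SD σ = 2 mm, positive meaning looser. Cuts are rounded the same way on both sides: -3.5, -1.5, 2.5 and 5.5 mm, with D above 10.5. Group sizes of 25 and 50 are both shown, because Section 5.0 gives 50 patients in total and the Synopsis gives 50 per group.

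**Step 3: grade shares.**

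P(A) = Φ((2.5 - μ)/σ) - Φ((-1.5 - μ)/σ)

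P(C) = Φ((-3.5 - μ)/σ) + Φ((10.5 - μ)/σ) - Φ((5.5 - μ)/σ)

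- PS +2: A = Φ(0.25) - Φ(-1.75) = 0.599 - 0.040 = 56%; C = 0.003 + 1.000 - 0.960 = 4%.
- MP -1.5: A = Φ(2) - Φ(0) = 0.977 - 0.500 = 48%; C = Φ(-1) + about 0 = 16%.
- PS +0.5: A = Φ(1) - Φ(-1) = 68%; C = 0.023 + 0.006 = 3%.
- MP -2: A = Φ(2.25) - Φ(0.25) = 0.988 - 0.599 = 39%; C = Φ(-0.75) + about 0 = 23%.
- PS +3: A = Φ(-0.25) - Φ(-2.25) = 0.401 - 0.012 = 39%; C = 0.001 + 0.106 = 11%.
- MP 0: A = Φ(1.25) - Φ(-0.75) = 0.894 - 0.227 = 67%; C = 0.040 + 0.003 = 4%.

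Means of +2 and -1 lie symmetrically about the middle of band A (0.5 mm). Both give 44% below A, so the share graded normal shows nothing of a 3 mm difference.

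**Step 4: what a test would conclude.** Trials were simulated with a Mann-Whitney test on grades at two-sided 0.05; simulation error is up to about 2 percentage points.

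| Assumed means (mm) | Rank test on Lachman grades, 25 per group | 50 per group |
|---|---|---|
| PS +2, MP -1.5 | MP worse in 13% | MP worse in 24% |
| PS +0.5, MP -2 | MP worse in 69% | MP worse in 93% |
| PS +3, MP 0 | MP better in 50%, worse in 0% | MP better in 83%, worse in 0% |

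In the first row, the chi-square test that Section 6.0 names for categorical data gives a significant result with MP worse in about 15% and 41%. With σ = 2.5 mm, the rank-test figures for that row are about 9% and 15%.

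**Step 5: the signed value.** The smallest true difference above is 2.5 mm. At 25 per group the standard error is 2 × √(2/25) = 0.566, so 2.5/0.566 = 4.42 and power is about Φ(4.42 - 1.96) = Φ(2.46) = 99%. The other cases are higher, so the signed value detects each difference in 99-100% of trials.

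**The case against.** Several points on the other side stand.

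- **The MP knee may not be tighter than the opposite knee.** Section 1.0 describes a design closer to normal that "reduces anteroposterior instability, and avoids condylar lift-off". It does not say that translation falls below that of a normal knee. A near-normal knee sits around 0, where the grade points the right way. The cost is then power, not direction.
- **Only one row is affected.** A reader might infer that the whole section 4 grade runs the wrong way. The documents do not support that: the other millimetre rows do not downgrade tightness, and the rule for combining rows (footnote 4) is not shown.
- **KT1000 is already planned.** A reader might infer that the trial has no sound measure of laxity. It has an instrumented one that does not depend on the Lachman boxes. The plan does not say how that measure relates to the grade.
- **Larger figures are possible.** Cutting the tight side at -1 and -3 while rounding the loose side to 2.5 and 5.5 gives 34% and 59% in the first scenario. That treats the two sides unequally, and those figures should not be used.
- **The reference is inferred.** The footnote defining the Δ mark is not in the documents. Reading it as a difference from the opposite knee rests on the negative bands and the opposite-knee fields. The main Lachman row is broken in the text available. The full bands come from the optional alternative row, and what survives of the main row agrees with it.
- **Negative values may never arise.** Section 5.0 names only the operative knee, so side-to-side scoring may not happen at all. That is a reason to state the procedure; it does not make the grade sound.

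**Conclusion.** The concern holds for the Lachman row. Its bands as printed are not monotone in laxity, and Section 5.0 uses them to grade stability. How much harm follows depends on where the operated knees lie relative to the opposite knee, which the documents do not say. Under an assumed SD of 2 mm, the chance of a significant result against a truly tighter MP knee runs from 0% (MP level with the opposite knee) to about 69% and 93% at 25 and 50 per group (MP 2 mm tighter, PS 0.5 mm looser). In the favourable case the grade still finds the difference in only 50% and 83%, against about 100% for the signed value.

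The documents do not show that the trial will favour the wrong implant, or that the overall section 4 grade is affected. The change is worth making before examinations begin, because a sign that is not recorded may not be recoverable.

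**What to change.** In Section 5.0, state that the same examiner tests the opposite knee at the same visit, as the form's side-to-side scoring implies. Have the examiner write the signed millimetre difference (positive = looser, negative = tighter) beside the Lachman row and the other millimetre rows. Say which box -1 mm belongs in. Complete the form's opposite-knee field, since Sections 3.1 and 3.2 set no condition on that knee.

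In Section 6.0, compare the signed values between groups as the examination measure, alongside the KT1000 values. Keep the A to D grade as descriptive, and count knees graded B or C for tightness separately from those graded for looseness.

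The cost is a brief examination of a second knee, one extra number per row and a few sentences of text, with no added visit or staff. Manual millimetre estimates are imprecise, but the examiner must already judge millimetres to choose a box.

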- Knee pathology: Date of onset, age of onset, any associated injuries, radiographic findings, dates and types of prior therapeutic interventions and their effectiveness.
- Physical exam: Specifically, the following information will be obtained: documentation of nerve function, strength, sensation, vascular status, pre-operative stability.
- Outcome data at final follow-up: Ambulatory aid use, orthosis use, job change as result of knee pathology, whether patient went back to work if applicable.

All data collected from chart review will be coded and noted on the Data Collection Form. All patient collected chart data as well as the PROMIS surveys will be coded. The data points will be identified by a random string of five numbers and letters that will be assigned by the PROMIS online database system.

Potential risks involved in this study include the inconvenience of completing questionnaires and stability testing, pain during stability testing, or a fall during the get up and go test. The patient's level of pain will be assessed on the visual analog scale prior to stability testing, and if the degree of pain is felt to be too great by the subject or examiner, the test will be deferred. Inquiry as to the patient's usual level of function will inform the appropriateness of the get up and go test. If the patient does not normally perform transfers into/out of chairs, then those analyses will be deferred. Any ambulation aids that the patient is accustomed to using will be made available.

One possible risk related to the patient's participation in this study is the loss of privacy. To reduce these risks, all of the information collected will be coded (the patient will be assigned a study number and all data will be linked to that number and not the patient's name) and stored in a password-protected file on a password-protected computer. Some of the questions asked may be upsetting, or the patient may feel uncomfortable answering them. If the patient does not wish to answer a question, they may skip it and go to the next question.

Additionally, both knee prostheses included in this study are in common use by orthopaedic surgeons today. Therefore, there are no additional risks involved in the use of these implants for this study.

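### Complications and reoperations are sought only in NMH and NMFF charts, so events treated elsewhere may go unrecorded, and no rule classifies patients without a charted event

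*Combined protocol and SAP*

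**What the plan says.** Section 5.0 states that "A prospective chart review will be performed starting at the time of enrollment and ending at the study completion date to obtain and verify" a list of items, and gives the source as "data from NMH Medical records (PRIMES, Cerner PowerChart) and NMFF Medical Records (EpicCare, IDX/GE Centricity". In that list "Complications/Reoperations" is a bare field, with no definition, grading or time window of its own. The list closes with "Outcome data at final follow-up: Ambulatory aid use, orthosis use, job change as result of knee pathology", followed by return to work.

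Patient-reported outcomes are scheduled immediately after surgery, at 6 weeks, at 3 months, and then "6 months post-operatively, 12 months post-operatively, and 2 years post-operatively". On how they are collected, the section says: "These questionnaires will be completed at the routine post-operative clinic visits or over the phone through PROMIS Assessment Center".

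Two study-specific assessments need the patient in person. One is the stability examination: "At 3-6 months post-op, the operative knee will be examined by a single Sports Orthopaedics attending surgeon". The other is the arthrometer reading, where KT1000 "measurements will also be taken by a single provider at the 3-month postoperative visit", with the get-up-and-go test done at the same time.

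Section 6.0 plans to summarize missing data and look for patterns, and to compare categorical variables by a Pearson chi-square or Fisher test. It gives no denominator, observation window or classification rule for complications.

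**The concern.** A chart shows only what reached that institution. An infection, a manipulation, a fall or a revision handled at another hospital enters the NMH or NMFF record only if the patient later attends and someone writes it down. After the 3-6 month examination nothing in the protocol requires that attendance, because the remaining questionnaires can be done by phone. Aid use, orthosis use and work status have the same weakness: a chart holds them only if someone asked.

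The study will already be in touch with these patients up to 2 years, yet no contact is described as including a question about complications or further surgery. At stake is whether the reported complication and reoperation rates can be read at face value. With groups this small, a single unrecorded event visibly changes a rate.

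**Working it through.** The documents state no event rate and no share of care received elsewhere, so there is no plan figure to reproduce. The check has two parts: what the text supports, and how sensitive the rates would be.

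**Coverage**

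1. *Sources named for complications and reoperations:* the NMH and NMFF records (Section 5.0). No patient question, outside-record request or registry is mentioned.
2. *Post-operative contacts:* immediate, 6 weeks, 3 months, 6 months, 12 months and 2 years, which makes six.
3. *Time with no required study visit:* the last in-person assessment falls at 3 to 6 months, and follow-up runs to 24 months. 24 − 6 = 18 months, or 24 − 3 = 21 months if the examination is done early.
4. *Do the questionnaires fill the gap?* The Oxford Knee Score, VR-12 and Forgotten Joint Score items shown in the appendices do not ask about a complication, hospital stay or further operation. Oxford item 10 asks about a feeling of giving way, not an event. The Knee Society Score, Kujala, PROMIS instruments and Data Collection Form are not in the text available, so nothing is claimed about them.

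**Sensitivity**

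5. *Arm size:* the Synopsis gives 50 per group; Section 5.0 gives 50 in total, half per arm, so 25. Both are carried because the documents do not settle which applies.
6. *One missed event:* 1/25 = 4 percentage points; 1/50 = 2 percentage points. This step needs no outside assumption.
7. *Illustration on assumed inputs:* let p be the true event risk per arm (5% to 15%), m the share of events treated elsewhere and never charted (10% to 30%), and n the arm size. Expected missed events over both arms are 2n·p·m, and the chance of missing at least one is 1 − (1 − p·m)^(2n).

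| n per arm | p, m | Expected missed | Chance of at least one |
|---|---|---|---|
| 25 | 5%, 10% | 50 × 0.005 = 0.25 | 1 − 0.995^50 = 22% |
| 25 | 15%, 30% | 50 × 0.045 = 2.25 | 1 − 0.955^50 = 90% |
| 50 | 5%, 10% | 100 × 0.005 = 0.5 | 1 − 0.995^100 = 39% |
| 50 | 15%, 30% | 100 × 0.045 = 4.5 | 1 − 0.955^100 = 99% |

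8. *Effect on a rate and on the comparison:* if unseen events were scored as none, the recorded risk would be p(1 − m), that is 70% to 90% of the true risk. With equal loss in both arms, a true 5% versus 20% at m = 30% becomes 3.5% versus 14%, a difference of 10.5 points instead of 15. If both arms had a true 10% and one arm alone lost 30% of its events, it would read 7% versus 10%, a spurious 3 points.

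**The case against.** The strongest reply is that the text is silent on the harm. A reader might infer that patients with nothing in the chart will be counted as event-free. No sentence says so: Section 6.0 gives no classification rule and does plan to summarize missing data. That objection stands, and the defect is the missing rule, not a wrong one.

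Other stronger readings also fail:

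- *That follow-up as a whole may be done by phone.* The phone option is stated for the questionnaires only. In-person assessment is planned at 3 and 3-6 months, so the exposure lies mainly after 6 months.
- *That outside events are certain to be missed.* They can reach the chart as history at a later clinic visit, and surgical history is itself a chart-review field. This safeguard is incidental, and weakest for patients reached by phone.
- *That complications are the trial's only safety outcome, or that Section 1.0 flags them for this comparison.* No safety outcome is designated, and the same list holds post-operative laboratory values and prosthesis position. The higher complication rates cited in Section 1.0 came from a comparison with a mobile-bearing knee. The cited trial against a posterior stabilized knee favoured the medial pivot.
- *That the comparison between arms is biased.* Both arms are randomized and have the same follow-up schedule. Differential loss is possible, but nothing in the documents shows it.

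It is also fair to say that the complication comparison is weak whatever is done. For an assumed 5% versus 20%, Fisher power with perfect capture is 20% at 25 per arm and 51% at 50 per arm. At 30% loss it falls to 7% and 30%. This limits what a test can show, but not the need for an accurate count: descriptive rates from a small trial are still read and quoted.

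**Conclusion.** The point holds as a gap in ascertainment. Section 5.0 relies on two institutions' charts for complications, reoperations and final status. It requires no study visit for the last 18 to 21 months of follow-up, and the plan leaves patients without a charted event, or with incomplete follow-up, unclassified. Complication rates may be understated.

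The only size that follows from the documents is the weight of one missed event: 4 points at 25 per arm or 2 points at 50. Everything beyond that rests on assumed event risks and assumed outside care, and is illustrative. The stated goals in Section 2.0 concern knee stability and complications are not named as a primary outcome, so this affects secondary and safety reporting rather than the main comparison. It merits correction because the remedy is cheap and an event not asked about at the time may be hard to recover later.

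**What to change.** Amend Section 5.0 and add a short rule to Section 6.0:

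- At each of the six scheduled post-operative questionnaire contacts, in clinic or by phone, ask one scripted question: since you last answered this, have you had any problem, fall, emergency visit, hospital stay or further procedure on the operated knee, here or elsewhere? Confirm positive answers from the chart or outside records. The first contact, immediately after surgery, will add little; the later ones carry the value.
- At the 2-year contact, collect aid use, orthosis use, job change and return to work directly from the patient.
- Report complication proportions by arm, with the number of patients who answered through 2 years as the denominator. Show patients with incomplete follow-up separately, with any events known among them. These are simple proportions, so the chi-square or Fisher test in Section 6.0 still applies and no time-to-event method is needed.

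The cost is a short amendment, a slightly longer questionnaire and occasional requests for outside records. Recorded complication rates will probably be somewhat higher. Treatment and the visit schedule do not change.
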